MedDRA	Medical Dictionary for Regulatory Activities	
mg	milligram	
MTD	Maximum tolerated dose	
NCI-CTCAE	National Cancer Institute-Common Terminology Criteria for Adverse Events	
OR	Objective Response	
ORR	Objective Response Rate	
PD	Pharmacodynamics	
PFS	Progression Free Survival	
PK	Pharmacokinetics	
PS	Physical performance	
PR	Partial Response	
RP2D	Recommended phase 2 dose	
SAE	Severe Adverse Event	

Abbreviations	Definition / Expansion
SAP	Satistical Analysis Plan
SD	Stable Disease
$T_{1/2}$	half-time
TEAE	Treatment-emergent Adverse Event
T_{max}	Time to maximum concentration
TTP	Time to Progression
ULN	Upper Limit of Normal

1. INTRODUCTION

The analyses described in this SAP are based upon the following study documents:

- Study Protocol, Version 1.6 (February 26, 2021)
- electronic Case Report Form, Version 6.0 (October 14, 2021)

2. STUDY OBJECTIVES

Primary Objectives

- To evaluate the safety and tolerability of single/multiple administration of GFH018 in patients with advanced solid tumors
- Determine the maximum tolerated dose (MTD) and/or recommended phase II dose (RP2D) of GFH018

Secondary Objectives

- To evaluate the pharmacokinetic characteristics of GFH018 after single/multiple administration in patients with advanced solid tumors
- To evaluate the preliminary efficacy of GFH018 in patients with advanced solid tumors
- To evaluate the expression level of TGF-β in the peripheral blood of patients with different solid tumors, and analyze whether it is related to the clinical response of subjects to GFH018

Exploratory Objectives

• Evaluate possible blood pharmacodynamic markers

3. OVERALL STUDY DESIGN

This is the first-in-human trial of GFH018, using an open-label, non-randomized, single/multi-dose dosing design to evaluate the safety, tolerability, pharmacokinetics, and preliminary anti-tumor efficacy of GFH018 in subjects with advanced solid tumors.

This study is divided into two parts: a dose-escalation part aimed at determining MTD and/or RDE followed by a dose expansion part to confirm the safety of RDE and RP2D and explore the preliminary efficacy of GFH018 in the potentially benefited population. The RDE will be determined for exploration in expansion. Different dosing regimens will be explored, RDE dose and optimal dosing regimen will be further confirmed, and RP2D will be obtained. Both parts were divided into three periods: screening, treatment, and follow-up.

Part I Dose Escalation

The study schema is shown in Figure 1 (14-day on/14-day off regimen).

[figure not shown]

Fig 1 Study Schema (Dose Escalation Part)

This part is a safety, tolerability, and pharmacokinetic study with a modified 3+3 design to determine MTD and/or RDE. According to preclinical data, the starting dose is selected as 10 mg/day (5 mg administered twice daily). In the first cycle, each group of subjects is given a single dose (5 mg as the starting dose) on day 1 and taken serial PK sampling. After the first dose on day 1, serial PK blood samples will be collected up to 72 h post-dose to obtain the complete PK profile of a single dose (the collection point design may be modified based on preliminary PK results). Subjects will be administered with GFH018 BID, 14d-on/14d-off from day 4. Four to six dose levels are planned (refer to Table 1). The first cycle is defined as 31 days, and subsequent cycles are all defined as 28 days. After the last dose of cycle 1 (day 17), serial PK blood samples will be collected to obtain PK characteristics at steady state. Starting from the third dose level, urine samples from steady state will also be collected for PK studies to fully understand GFH018 PK characteristics.

Table 1 Dose escalation	regimen	(provisional	dose level)

Dose level	Regimen	Incremental percentage (%)
1	5 mg bid, 14-d on/14-d off	-
2	10 mg bid, 14-d on/14-d off	100
3	20 mg bid, 14-d on/14-d off	100
4	30 mg bid, 14-d on/14-d off	50
5	40 mg bid, 14-d on/14-d off	33
6	50 mg bid, 14-d on/14-d off	25

During the study, a Safety Monitoring Committee (SMC) composed of principal investigators, representatives of contract research organizations (CROs) and sponsor representatives will be established to review the safety data generated in the study, mainly including Dose Limiting Toxicity (DLTs) and all other grade 2 and above adverse events per CTCAE v5.0, as well as pharmacokinetic and pharmacodynamic data, to determine whether to escalate to the next dose level. For a more specific dose escalation decision process and definition of DLT, see Section 5.4 of Protocol V1.6, "Study Drug Dose Escalation Methods".

SAP

The MTD is defined as the highest dose $\leq 1/3$ of the incidence of DLT. Once the MTD is reached, the dose will not be escalated under this dosing regimen (even if not all planned dose groups have been completed), and the SMC will review and decide whether to explore alternative dosing regimens, such as 7d-on/7d-off, or daily or other dose regimens (if the total daily dose is higher than or equal to the MTD within 28 days, the dose level needs to be lowered for daily or other dosing regimen exploration); On the other hand, if the MTD is not reached by escalating to the current highest dose level, the SMC will comprehensively evaluate all the data obtained to decide whether to proceed with a higher dose level exploration, such as 65 mg BID, 85 mg BID, etc.

The RDE will be determined by SMC based on comprehensive data such as safety and tolerability, PK, pharmacodynamics, and preliminary antitumor efficacy obtained during the dose escalation part.

At the end of the dose escalation, at least six evaluable subjects in the MTD/RDE group should be ensured.

Part II Dose Expansion

The primary objective of this part is to confirm the safety of RDE dose and explore different dose regimens to ultimately determine RP2D. The secondary objective is to initially explore the efficacy in potentially benefited populations.

The 14d-on/14d-off and 7d-on/7d-off dose regimens under RDE dose will be explored based on the data from the dose escalation part, while the SMC will review the safety, PK, and biomarker data then decide whether to also explore other dose regimens at RDE, such as daily dosing. This part will further confirm the safety of RDE dose and optimal dose regimen and obtain RP2D. At least 12 subjects (including subjects receiving the same dose during the dose escalation part) are required to be enrolled to determine the final RP2D.

Potential benefited tumor types will be selected for dose expansion part based on the mechanism of action of the drug and preliminary efficacy data in dose escalation part, including hepatocellular carcinoma, cholangiocarcinoma/gallbladder cancer, colorectal cancer, urothelial cancer, pancreatic, cervical, head and neck squamous cell or esophageal cancer, and nasopharyngeal carcinoma.

4. STUDY ENDPOINTS

4.1. Safety Variables

4.1.1. Adverse Events

Adverse events (AEs)

The definition of AEs can be found in the section 8.1 of protocol. AEs should be collected from the time of informed consent through follow-up. The follow-up period was 30 days (\pm 3 days) after discontinuation of study treatment. SAEs occurring during the follow-up period should be reported to the sponsor by routine methods.

Treatment emergent adverse events (TEAEs)

TEAEs are defined as adverse events that worsened or occurred following the first dose date of study treatment and within 30 days of the last treatment. If missing dates or time prevent a clear determination as to whether AE is treatment emergent, the adverse event will be regarded TEAE.

Treatment related adverse events

Treatment related AEs are defined as TEAEs definitely related, possibly related to study treatment, and the relationship unable to determine.

Serious adverse events (SAEs)

The definition of AEs can be found in the section 8.2 of protocol.

Treatment related SAEs

Treatment related SAEs are defined as SAEs definitely related, possibly related to study treatment, and the relationship unable to determine.

Adverse event of special interest (AESI)

According to the toxicological results of GFH018, ASEIs include elevated cardiac biomarkers BNP or troponin, and abnormal cardiac ultrasound.

Adverse events leading to interruption of study treatment

Adverse events leading to dose reduction of study treatment

Adverse events leading to discontinuation of study treatment

Severity of adverse events

Severity of all AEs will be graded according to CTCAE v5.0 with grade 1 to 5.

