7.5. Dose-determining Set (DDS)

DDS: consists of all subjects who have received at least 80% of the total planned dose of GFH018, are considered to have sufficient safety evaluation during the 31-day-observation period or developed DLT during the first cycle.

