8.2.6. Prior and Concomitant Medications and Surgeries/Procedures

Prior and concomitant medications will be coded using World Health Organization Drug Dictionary (WHO DD) version 202203 B3. Prior and concomitant surgeries and procedures will be coded using the Medical Dictionary for Regulatory Activities (MedDRA) version 25.0.

Prior and concomitant medications

SAP

Prior medications include non-study medications that started and ended prior to the first dose of study medication. Concomitant medications include non-study medications with start date on or after the date of the first dose of study medication and no later than 30 days after the last dose of study medication. Medications will be considered both prior and concomitant if the start date of the medication is prior to the first dose of study medication and the end date is on or after the first dose of study medication.

If the start date and/or end date of a non-study medication is missing or partially missing, the noncomplete date should be compared to the first dose date of study medication whenever possible. Non-study medication will be considered as concomitant medication unless there is clear evidence that the start date of the non-study medication is earlier than the first dose date of study medication. If there is clear evidence that the start date of the non-study medication is earlier than the first dose date of study medication, the non-study medication will be considered both prior and concomitant unless there is clear evidence that the end date is earlier than the first dose date of study medication. If there is clear evidence that the end date of the non-study medication is earlier than the first dose date of study medication, then the non-study medication will be considered as prior medication.

Prior and concomitant medications will be summarized by Anatomic Therapeutic Chemical (ATC) Grade 4 and Preferred Term (PT) and listed in detail for subjects in the FAS.

Prior and concomitant surgeries/procedures

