8.4.1. Adverse Events

Adverse events (AEs) will be coded using MedDRA version 25.0.

AE summary tables will include only TEAEs, while listings will include all AEs; AE incidence will be calculated based on the number of subjects with adverse events, and when a subject experiences multiple occurrences of the same AE under the same SOC and PT, the occurrence with the most severe grade will be counted. The following summaries and listings will be provided for AEs:

- Summarize the number and percentage of subjects with TEAEs, TEAEs with CTCAE Grade ≥ 3, treatment-related adverse events (TRAEs), TRAEs with CTCAE Grade ≥ 3, serious adverse events (SAEs), treatment-related serious adverse events (TRSAEs), AESI, DLT, TEAEs leading to treatment interruption, TRAEs leading to treatment interruption, TEAEs leading to dose reduction, TRAEs leading to treatment discontinuation, and TRAEs leading to treatment discontinuation.
- Summary of TEAEs by SOC, PT, and CTCAE Grade
- Summary of TRAEs by SOC, PT, and CTCAE Grade
- Summary of SAEs by SOC, PT, and CTCAE Grade
- Summary of TRSAEs by SOC, PT, and CTCAE Grade
- Summary of AESIs by SOC, PT, and CTCAE Grade
- Summary of TEAEs of Grade 3 or Higher by SOC, PT, and CTCAE Grade
- Summary of TRAEs of Grade 3 or Higher by SOC, PT, and CTCAE Grade
- Summary of DLTs by SOC, PT, and CTCAE Grade
- Summary of TEAEs leading to treatment interruption by SOC, PT, and CTCAE Grade
- Summary of TRAEs leading to treatment interruption by SOC, PT, and CTCAE Grade
- Summary of TEAEs leading to dose reduction by SOC, PT, and CTCAE Grade

- Summary of TRAEs leading to dose reduction by SOC, PT, and CTCAE Grade
- Summary of TEAEs leading to treatment discontinuation by SOC, PT, and CTCAE Grade
- Summary of TRAEs leading to treatment discontinuation by SOC, PT, and CTCAE Grade
- Summary of TEAEs by PT and CTCAE Grade, ordered in descending frequency
- Summary of TRAEs by PT and CTCAE Grade, ordered in descending frequency
- Summary of cause of death
- Listing of adverse events
- Listing of SAEs
- Listing of AESIs
- Listing of DLTs
- Listing of TEAEs leading to treatment interruption
- Listing of TEAEs leading to treatment discontinuation
- Listing of deaths

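### The TEAE window opens after the first dose date rather than at the first dose, so an adverse event dated Day 1 can drop out of the TEAE-only summary tables

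*SAP*

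**What the plan says.** **TEAE definition (SAP Section 4.1.1).** "TEAEs are defined as adverse events that worsened or occurred following the first dose date of study treatment and within 30 days of the last" dose. A fallback follows: "If missing dates or time prevent a clear determination as to whether AE is treatment emergent, the adverse event will be regarded TEAE".

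**What depends on it.** Treatment-related events are a subset: "Treatment related AEs are defined as TEAEs definitely related, possibly related to study treatment", together with those whose relationship cannot be determined. Section 8.4.1 then states: "AE summary tables will include only TEAEs, while listings will include all AEs".

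**How Day 1 is used (Section 3, Part I).** In the first cycle, "each group of subjects is given a single dose (5 mg as the starting dose) on day 1", with serial PK sampling up to 72 hours. After that, "Subjects will be administered with GFH018 BID, 14d-on/14d-off from day 4".

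**How the SAP words a similar boundary elsewhere (Section 8.2.6).** "Concomitant medications include non-study medications with start date on or after the date of the first dose of study medication". Concomitant surgeries and procedures follow the same pattern.

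**The concern.** An event dated on the first dose date does not, in the ordinary sense of the word, follow that date. A program that turns the sentence into onset date > first dose date will set the TEAE flag to no for a Day 1 onset. The medication rule in the same SAP, programmed from its own text, becomes start date >= first dose date. A medication started on Day 1 to treat a Day 1 reaction would then be tabulated as concomitant, while the reaction itself would not be tabulated.

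Safety and tolerability is a primary objective, and this is a first-in-human trial. In escalation, Day 1 is the subject's first exposure, given as a single dose with no further dosing until Day 4. Acute reactions to that exposure would carry the Day 1 date. If they are left out of the incidence tables, the tables under-report part of what the study was set up to measure.

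**Working it through.** The SAP gives no figure to reproduce here, and Section 5 says no hypothesis is tested. The check is to apply the wording under its two possible readings and then size the effect of one omitted subject.

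**Step 1: the two readings.**
- Reading A (date only): TEAE if onset or worsening date > first dose date.
- Reading B (date and time): TEAE if onset or worsening is after the date and time of the first dose. If a missing time leaves this unclear, the fallback makes it a TEAE.

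Both keep the end of the window at 30 days after the last treatment.

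**Step 2: classify the cases, with Day 1 as the first dose date.**

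| Event | Reading A | Reading B |
|---|---|---|
| Day 1, time known, after the dose, does not worsen later | not a TEAE | TEAE |
| Day 1, time missing, does not worsen later | not a TEAE | TEAE (fallback) |
| Day 1, time known, before the dose, does not worsen later | not a TEAE | not a TEAE |
| Day 1 onset, worsens on a later date | TEAE | TEAE |
| Onset on Day 2 or later | TEAE | TEAE |

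The readings part in the first two rows only. In row 2 the fallback does not help under Reading A: the onset date is known and equals the first dose date, so nothing is unclear and the fallback is not triggered.

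**Step 3: follow the flag into the tables.** A row 1 or row 2 event under Reading A is not a TEAE. It cannot be a TRAE, since TRAEs are defined within TEAEs. Under the general sentence in Section 8.4.1 it is also left out of the other tables restricted to TEAEs, and it remains in the listings, which hold all AEs.

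**Step 4: size per omitted subject.** Assume the subject has no other qualifying event in the table row concerned. The change in incidence is 1/n. Cohort sizes come from Section 6: 3-6 in escalation, and at least 12 at the RP2D.
- n = 3: 1/3 = 33.3 percentage points
- n = 6: 1/6 = 16.7 percentage points
- n = 12: 1/12 = 8.3 percentage points, and less with more subjects

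As an illustration, take a cohort of 3 in which one subject has drug-related vomiting 4 hours after the Day 1 dose and no later event. Reading A reports TRAEs in 0/3, and Reading B reports 1/3.

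**The case against.** The strongest reply is that the fallback sentence shows what was meant. A missing time can matter only on a boundary day. Under Reading A the word *time* would do nothing at the start of the window, so a fair reader takes the comparison as date and time, and Day 1 post-dose events stay in. Other wording points the same way: Section 8.1 anchors baseline on the first administration, and Section 8.4.2 counts laboratory shifts from the start of treatment. This argument stands as evidence of intent. It does not settle the rule, because the definition itself names only a date and gives no dose time to compare with.

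Some stronger readings are tempting, and the SAP does not support them:

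- **That every Day 1 event is lost.** A Day 1 event that worsens on a later date qualifies under either reading, and under Reading B post-dose Day 1 events stay in.
- **That dose escalation or the MTD is affected.** Section 3 has the Safety Monitoring Committee review DLTs and all other grade 2 and above events, with no TEAE filter. The DLT analysis uses the Dose-determining Set, which includes subjects who "developed DLT during the first cycle", and that cycle includes Day 1. The DLT definition is left to the protocol. DLTs are among the tables listed in 8.4.1, but that alone does not show that DLT counting depends on the TEAE flag.
- **That Section 8.2.4 supplies a second contrast.** Its *on or after* wording classifies medical conditions by when they ended, so it is not a start-date rule. The contrast rests on 8.2.6 alone.

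It is also fair to say that the larger percentages come from the smallest cohorts, and that the stand-alone Day 1 dose is described for escalation only.

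**Conclusion.** The point holds as a defect of wording with a real risk of under-reporting, not as a certain exclusion. The definition is anchored on a date, and the sentence after it presupposes a time. A program written from the first sentence drops Day 1 events that do not worsen later, and one written from both sentences together keeps those that follow the dose. For a flag that governs the main safety tables, the SAP should allow only one result.

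The size is 17 to 33 percentage points per omitted subject in cohorts of 6 to 3, and at most 8.3 points with 12 or more. This rests on three assumptions: the program uses dates only, the event begins on Day 1 and does not worsen later, and the subject has no other event in the same row. How many events meet these conditions is unknown. The document also does not show whether the case report form records AE onset times. The definition applies to both parts of the study, but Day 1 carries particular weight in escalation. The listings keep all events.

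**What to change.** Replace the definition in Section 4.1.1 with wording such as: AEs that start, or worsen in grade, at or after the date and time of the first administration of study treatment and up to 30 days after the last dose; an AE with onset on Day 1 is treatment-emergent unless its onset is known to precede the dose.

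TRAEs and the TEAE-only tables in 8.4.1 then follow without further edits. No change to the DLT boundary is proposed here, because that definition belongs to the protocol.

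The cost is one sentence of SAP text and one programming condition. The downside is that a few pre-dose Day 1 events with no recorded time will be counted as TEAEs. That is conservative, and it agrees with the SAP's own rule of resolving doubt from missing times towards TEAE. If a date-and-time comparison was always intended, the change only states it.

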4.1.2. Laboratory Tests

Please see Table 2 for the laboratory tests parameters.

Table 2 Laboratory tests parameters

Laboratory tests	Parameters
Hematology	Red blood cell count (RBC), hemoglobin concentration (HGB), hematocrit (HCT), mean red blood cell volume (MCV), mean red blood cell hemoglobin content (MCH), mean red blood cell hemoglobin concentration (MCHC), white blood cell count (WBC), platelet count (PLT), neutrophil count (ANC), lymphocyte (LY) count, monocytes (MO) count, eosinophil (EO) count, Basophil (BA) count, percentage neutrophils, percentage lymphocytes, percentage monocytes, percentage eosinophils, percentage basophils
Urinalysis	Urine leukocytes (LEU), urine nitrite (NIT), urine pH, urine specific gravity (SG), urine protein (PRO), urine glucose (GLU), urine ketone bodies (KET), urine bilinogen (UBG), urine bilirubin (BIL), urine occult blood (BLD), 24-hour protein*
Coagulation function	Prothrombin time (PT), activated partial thromboplastin time (APTT), international normalized ratio (INR)
Chemistry	Aspartate aminotransferase (AST), alanine aminotransferase (ALT), alkaline phosphatase (ALP), lactate dehydrogenase (LDH), glutamyl transpeptidase (GGT), urea (UREA)/urea nitrogen, blood creatinine (CREA), total protein (TP), albumin (ALB), white globular ratio (A/G ratio), total bilirubin (TBIL), direct bilirubin (DBIL), creatine kinase (CK), pancreatic amylase (AMY), fasting blood glucose (FPG), total cholesterol (TCHO), low-density lipoprotein cholesterol (LDL-C), high-density lipoprotein cholesterol (HDL-C), triglycerides (TG), bicarbonate, phosphate, calcium, sodium, chloride, potassium
Virus testing	Hepatitis B surface antigen (HBsAg), hepatitis C virus antibody (anti-HCV), HIV antibody, treponemal antibody
Thyroid function tests	Free triiodothyronine (FT3), free thyroxine (FT4), and thyroid-stimulating hormone (TSH).
Cardiac markers	Hypertroponin T (or Hypertroponin I), brain natriuretic peptide (BNP), hs-CRP, cysteine protease inhibitor (Cystatin C)
Pregnancy test	Serum β-HCG pregnancy test (blood pregnancy test in women of childbearing age)

^{*} For routine urinalysis, if the result of the fibrine test strip for urine protein is \geq 2+, a 24-hour urine sample should be collected for analysis.

4.1.3. Electrocardiogram (ECG)

ECG includes hearts rate, PR, QRS, QT, QTcF, and the clinical interpretation.

4.1.4. Echocardiography

Include left ventricular ejection fraction, heart valve function, and clinical interpretation.

4.1.5. Physical Examination

Physical examination includes General condition, skin condition, head/neck, lungs, cardiovascular, liver, kidneys, gastrointestinal, lymphatic system, musculoskeletal system, limbs, larynx; and weight.

4.1.6. Vital Signs

Vital signs include temperature, blood pressure, heart rate, and respiratory rate.

4.1.7. Eastern Cooperative Oncology Group (ECOG) Performance Status

Score	Criteria	
0	Fully active, able to carry on all pre-disease performance without restriction.	
1	Restricted in physically strenuous activity, but ambulatory and able to carry out work of a light or sedentary nature (e.g., light housework, office work).	
2	Ambulatory and capable of all self-care, but unable to carry out any work activities. Up and about more than 50% of waking hours.	
3	Capable of only limited self-care, confined to bed or chair more than 50% of waking hours.	
4	Completely disabled. Cannot carry on any self-care. Totally confined to bed or chair.	
5	Dead.	

